**Table 7: Tracking Measures Using *RE-AIM Framework* Approach**

RE-AIM	Evaluation Question	Tracking Measures	Data Source
Adoption	How were community partners and primary care settings engaged in the study?	# of participating community partners and primary care settings (offices, health centers). Primary care offices' satisfaction with participation.	Contact log  On-site observations On-site interviews

Reach	To what extent are high risk target populations being reached?	Patient characteristics (demographics, insurance status, ocular history, ocular risk factors).	Intake form/EMR
Implementation	How was the program implemented?	Patient navigator, cultural competency training conducted. # of staff at each onsite activity. # of patients who follow up with general ophthalmologists. Time taken per patient and for each eye exam. # of confirmatory diagnosis from fundus photos. # of referrals made based on NEI-VFQ.	Planning log  On-site observations  EMR
Efficacy/ effectiveness	Did the intervention work? (Comparison between intervention and control groups)	# of patients from each group adhering per year. Average percentage of visits attended per year. Clinical measures (visual acuity, IOP, VF). Health related quality-of-life (Visits 2 and 8). Satisfaction with eye services at each visit.	EMR  EMR NEI-VFQ Patient satisfaction survey
Maintenance	To what extent has the program been institutionalized?	Willingness of partners and PCPs to continue with telemedicine and community model.	On-site interviews

## E. Outcome Assessments and Comparators for Analysis

E.1.a. Tracking Outcome Performance: We are committed to implementing a comprehensive process and outcome evaluation to monitor and track all outcome performances and identify best practices to replicate and disseminate efforts (Table 8). Investigators in collaboration with CDC and Westat, have created an evaluation plan containing specific, measurable, achievable, realistic, and time-limited (SMART) goals. The biostatistician will clean and manage the data. Our evaluation will be consistent with the CDC’s *Framework for Program Evaluation*. We anticipate that the results will be generalizable and that our study can serve as a framework for similar interventions elsewhere.

E.1.b. Summative and Formative Evaluation Plan: We will assess measurable, immediate and long-term outcomes and develop a comprehensive plan for dissemination. With the assistance of Westat, all evaluation tools and reports produced will harmonize with other CDC Cooperative Agreements. Wills Eye will track data on individuals and on the intervention to understand the success, limitations, timeliness, and effectiveness of the project. We have created data collection tools to track data at all levels of the study. On-site tracking will be conducted by trained ocular technicians, study staff, and primary care and ophthalmology office staff. Using a customized, HIPAA compliant, NextGen EMR template, all participants will be assigned a unique medical record number (MRN). This number will be linked to each exam and include all clinical variables. Final diagnosis, proposed treatment, and follow-up recommendations will be documented.

E.1.c. Data Management/Quality Assurance: Exam results and treatment dates will be linked with MRNs and stored in a password-protected, encrypted, hard drive. The biostatistician and data manager, using SAS software, will create a separate list linking patient names and exam and treatment dates. To track follow-up adherence and scheduling, we will document on EPM the exam/treatment dates. We will also note the number of follow-up visits that each patient schedules, keeps, reschedules, cancels, and misses. The project manager will also monitor and store results, such as the NEI VFQ-25 and the satisfaction survey. De-identified, aggregated data will be sent to Westat in an Excel spreadsheet. Upon completion of the project, all data and databases will be securely housed for 3 years. Wills Eye Hospital will maintain the confidentiality of records according to the provisions of Title 42 of the Code of Federal Regulations, Part II. (See Table 8)

### Table 8: Process Measures to Be Tracked

Process Measures	Phase 1 Plan, Develop Detection	Phase 2 Confirm Diagnosis Follow-up	Phase 3 Follow-Up Disseminate Replicate
# of partners and primary care offices for recruitment sites	✓		
# of patients received by each primary care offices and health centers	✓		
# of letters mailed/calls made to patients from recruitment and Visit 1	✓		
# of patients scheduled, confirmed, attended detection eye exam Visit 1-2	✓	✓	
# of patients who cancelled and assessment of barriers to attending exam	✓	✓	✓
# of patients/doctors sent letters with normal/abnormal eye exam results	✓	✓	✓
# of patients diagnosed with glaucoma, suspect, and other eye diseases	✓	✓	✓
# of patients who attended exams with an ophthalmologist (Visits 3-8)		✓	✓
# of patients recommended to follow-up in 1-2 weeks, 1-2 months, 3-6 months, 6 months, and 12 months from baseline Visits 2-8		✓	✓
# of people prescribed ocular medication, laser therapy, or eye surgery		✓	✓
# of patients who requested medication assistance for eye drops	✓	✓	✓
# of patients who requested and used translation/interpreter services	✓	✓	✓
# of patients who requested and used transportation services	✓	✓	✓
# of referrals for a low-vision specialist, cataract surgeon, etc.		✓	✓
# of referrals for a Medicare/Medicaid advisor or to complete application		✓	✓

**E.1.d. Patient Satisfaction Surveys:** With Westat, the CDC and Advisory Board members, we will develop brief questions regarding the patient's satisfaction. We will survey patients at the conclusion of all visits. Wills Eye research staff will administer surveys during the detection and baseline visits. We hypothesize that satisfaction will be greater for those in the intervention group than in the usual care group.

## **E.2. Data Analysis for Aims 1 and 2**

**E.2.a. Primary Analysis for Aim 1:** The primary analysis for Aim 1 will be to estimate the positive predictive value (PPV) of the teleophthalmology intervention for diagnosing of glaucoma. We hypothesize that the diagnosis of glaucoma and glaucoma suspect using undilated optic disc images, tonometry pressure results, and medical history will predict the comprehensive eye exam diagnosis. That is, we will calculate the proportion of patients diagnosed with glaucoma or glaucoma suspect whose diagnosis was confirmed at Visit 2 with an exact two-sided binomial confidence interval. We will conclude that the telemedicine intervention has good performance if the lower bound of the confidence interval is above 80%.

The expected sample size for this aim is 250 patients as we anticipate approximately 50% of those diagnosed with eye pathology and who return for the confirmation Visit 2 will have been diagnosed with glaucoma or glaucoma suspect at Visit 1. Data from Maa (2014) can be used to estimate the PPV for glaucoma at 85%. With 250 patients, we have 50% power to conclude the PPV is greater than 80% if the true PPV is 85% and over 99% power to conclude the PPV is greater than 80% if the true PPV is 90% using a 2-sided test with alpha=0.05. We will repeat this analysis looking at the proportion of patients diagnosed with eye pathology who in fact have an ocular diagnosis (whether or not the exact abnormality was correct).

**E.2.b. Primary Outcome Measure for Aim 2:** Patient baseline demographic and clinical characteristics will be summarized overall and by randomization assignment (in Aim 2) using means, medians, standard deviations, and ranges or frequencies and percentages, as appropriate. Our general approach from the randomized trial is to analyze patients as randomized regardless of the amount of intervention received. The primary outcome measure for Aim 2 is attendance at recommended follow-up visits (Visit 4 and later). Since the expected

number of appointments will differ based on diagnosis and disease severity, which may change over time, attendance will be summarized annually.

For each year under observation, an expected number of visits will be determined based on the recommended follow-up at the first visit for that year (Table 9). For purposes of this calculation, attendance at appointments within 13 months of the first visit will be assessed. We recognized that follow-up recommendations will vary for each patient depending on eye pressure control, medication adherence, disease severity, and surgery/laser appointments. Therefore, the research team, in conjunction with [name] and the CDC, will plan and develop definitions of adherence for patients during Visits 3-8.

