#### **C.4. Research Design and Methods**

**C.4.a: Project Overview:** The Wills Eye Glaucoma Research Center will conduct a 5-year prospective, randomized controlled trial to evaluate an innovative, community intervention using posterior fundus photographs of the optic nerve and macula to improve access and utilization of eye care to detect, treat, and manage high-risk patients with previously undiagnosed glaucoma, glaucoma suspect, and other eye diseases. L. [name]; [name]; and [name], RD, will lead the research study.

Our diverse targeted, at-risk population includes African Americans, Hispanics, and Asians over age 40; other older adults (aged 65+); individuals over age 40 with a family history of glaucoma and/or with diabetes. Approximately 1250 patients will be recruited from geographically diverse locations across Philadelphia and Chester counties, with the help of our community partners. **Phase 1** will consist of detecting eye disease in 7

primary care offices and 10 FQHC using telemedicine (Visit 1), followed by a comprehensive eye exam by a Wills glaucoma specialist in the same setting to confirm the diagnosis (Visit 2). Based on preliminary data, 30% of patients (approximately 750) will have abnormal optic nerve and/or macula images. The predictive accuracy of the optic nerve images to detect glaucoma and glaucoma suspect as confirmed by the comprehensive eye exam will be evaluated.

**Phase 2** will involve consenting, enrolling, and randomizing 374 patients to either the usual care group (n=187) or the enhanced intervention group (n=187). The enhanced intervention will consist of using patient navigators and a social worker to reduce barriers to follow-up eye care. **Phase 3** will consist of following patients proximally (6 months) and distally (3 years) while they attend appointments with a local, eye care provider (Visits 3-7). Adherence to follow-up recommendations for eye care will be the primary outcome measure. A comprehensive cost study to estimate the intervention costs and cost-effectiveness of detecting eye diseases and vision impairment in a high-risk population will also be conducted. Protocols, materials, outcomes, and results will be disseminated to other communities in order to expand detection of glaucoma, other eye diseases, and visual impairment, and to further refine these approaches to successfully scale the program up to a national level.

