NOTE: During Visit 1 if the IOP is elevated based on the criteria outlined below by glaucoma specialists, the subject will be asked to skip Visit 2 and will be eligible to continue to Visit 3 with the local ophthalmologist. The subject will sign the Part II consent and get randomized during Visit 1. They will also complete the NEI-VFQ-25. If the subject chooses not to continue with the study, the team along with the PCP will make sure to stress the importance of seeing an ophthalmologist of their choosing in the time frame outlined.

IOP in either eye  $> 30\text{ mm Hg}$  subject to visit ophthalmologist within 2 weeks  
 IOP in either eye  $> 35\text{ mm Hg}$  subject to visit ophthalmologist within 1 week  
 IOP in either eye  $> 40\text{ mm Hg}$  subject to visit ophthalmologist within 1 day

A Wills Eye Hospital ophthalmologist will call a local eye care provider to advise them of the elevated eye pressure and the need for a timely appointment.

When images are received at WETD, a trained reader reviews the data and confers with the glaucoma and/or retina specialist, who determines if clinical pathology merits further evaluation and treatment and establishes relevant diagnoses. In addition to glaucomatous changes and DR, ocular hypertension, cataract, branch retinal vein and arterial occlusion, central retinal vein and arterial occlusion, epi-retinal membrane, macular degeneration, drusen and pigmentary disturbance will be documented on the report. Reports (Appendix F) are

uploaded to a secure password-protected, HIPAA-compliant web site, where the PCPs can access these records and link the report to their own patient’s medical record. Patients with ocular pathology or patients who have photographs that are unreadable will be contacted and scheduled within 1-2 months for Visit 2 to confirm the diagnosis. Any patient with emergency eye issues, such as a detached retina, will be called immediately and scheduled for Visit 2. The patient’s PCP will also be notified by phone immediately and a follow-up letter will be sent to the patient’s home.

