**C.5.d. Ongoing Education/Training/Fidelity:** Extensive training will take place during Phase 1 to ensure that all research staff adhere to policies and procedures. The Director of the Department of research and Glaucoma research center will be responsible for training Wills Eye Department of Research staff in cultural competency. The Director of Operations for Wills Eye Hospital’s Telemedicine Department will be responsible for ongoing training on the Volk Pictor Plus camera for all ocular technicians and study staff. Glaucoma specialists will be trained to read the optic nerve images. Study Investigators will develop letters to send to local ophthalmologists to inform them about the study and invite them to participate. In addition, but before we begin the study, in conjunction with our general ophthalmology advisor, we will plan and develop definitions of adherence for all patients during Visits 3-8.

**C.6. Visit 2: Baseline Assessment Measures and Confirming Diagnosis (PCP Office):** Patients who have been diagnosed with glaucoma, glaucoma suspect, other eye diseases, vision impairment or have photographs that are unreadable who require non-emergent follow-up, will be notified by mail and telephoned by the study staff to schedule Visit 2 within 4 weeks of the detection visit. We will call all patients to remind them of the exam, discuss steps to prepare for an eye exam, and answer any questions. There will be no cost for this comprehensive eye exam. Any patient with an emergency eye issue at Visit 2 will be contacted immediately by phone and scheduled for an appointment at Wills Eye Hospital.

To conduct Visit 2, a leased van will transport the research team and all necessary equipment to the site each day. During the visit, an ocular technician and a glaucoma specialist will assess the patient’s ocular, systemic, and family history and conduct a undilated eye exam including: 1) visual acuity measurement using Snellen eye charts, 2) slit-lamp biomicroscopy of the anterior segment, 3) IOP, 4) undilated optic nerve head evaluation (although if patient has diabetes they may be dilated),5) central corneal thickness measurement, 6) visual field analysis using the Octopus visual field analyzer and 7) gonioscopy.

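### Nothing in the available plan keeps the Visit 2 examiner from knowing, or having helped make, the Visit 1 call that Visit 2 verifies in Aim 1

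*Combined protocol and SAP*

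**What the plan says.** Section E.2.a defines the Aim 1 estimand: "we will calculate the proportion of patients diagnosed with glaucoma or glaucoma suspect whose diagnosis was confirmed at Visit 2". Good performance is concluded "if the lower bound of the confidence interval is above 80"%, using an exact two-sided binomial interval and an expected 250 patients. No other reference standard enters this analysis. Section C.9 has Visit 3 providers reconfirm diagnoses, but E.2.a does not use that.

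Visit 2 is described by its purpose. Section C.4.a has the examination done "by a Wills glaucoma specialist in the same setting to confirm the diagnosis (Visit 2"). Section C.5.c says that patients with pathology or unreadable photographs "will be contacted and scheduled within 1-2 months for Visit 2 to confirm the diagnosis". Section C.6 says that "an ocular technician and a glaucoma specialist will assess the patient" and lists the tests.

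Under C.5.c, a trained reader confers with a glaucoma and/or retina specialist, who establishes the Visit 1 diagnosis. C.5.d has glaucoma specialists trained to read the optic nerve images. No rule says that the Visit 2 examiner must be a different person, or must not see the Visit 1 images or report.

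The one blinding provision for this study is in C.9. It covers the local eye care providers and the randomized group. The single-blind trial in C.3.b is an earlier diabetes study.

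**The concern.** When the reference diagnosis is made by someone who knows the index result, agreement between the two partly reflects expectation. A specialist who knows that the photographs were called glaucoma suspect may settle a borderline disc toward that call, and a specialist who made the call may be more inclined to stand by it. Either would raise the PPV.

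There is some room for this. The criteria in C.6 include suspicious discs, a cup-to-disc ratio above 0.5, asymmetry above 0.2, and a combination of pressure and disc appearance. For most patients the nerve is judged undilated. Estimates near a cut-off take judgement.

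At stake are the Aim 1 estimate and the 80% rule attached to it. The order in which a diagnosis is recorded cannot be reconstructed once the examinations are done.

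**Working it through.** **Inputs (E.2.a).** n = 250; exact two-sided 95% interval; success if the lower limit exceeds 0.80; planning PPV 85%; stated power 50% at 85% and over 99% at 90%.

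**Step 1: the success count.** The Clopper-Pearson lower limit for x confirmed of n is the 0.025 quantile of a Beta(x, n − x + 1) distribution.
- x = 212: 0.7974, fails.
- x = 213: 0.8018, passes.

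Success therefore means at least 213 of 250, or 85.2%.

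**Step 2: the plan's own figures.** P(X ≥ 213 | 250, p) is 50.8% at p = 0.85 and 99.4% at p = 0.90. Both stated powers reproduce. At p = 0.80 the chance of success is 2.1%.

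**Step 3: illustration of review bias.** Let p be the PPV that a masked examiner would find. Let f be the share of false positives confirmed because the examiner knew the Visit 1 call. The apparent PPV is

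q = p + f(1 − p),

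and the chance of success is P(X ≥ 213 | 250, q). The documents give no value for f, so every value below is an assumption.

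| True PPV p | f = 0 | f = 5% | f = 10% | f = 20% | f = 30% |
|---|---|---|---|---|---|
| 80% | 2.1% | 5.0% | 10.7% | 33.9% | 68.2% |
| 78% | 0.3% | 0.9% | 2.5% | 13.9% | 43.8% |
| 75% | 0.01% | 0.03% | 0.15% | 2.1% | 14.9% |

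Two cells worked through:
- p = 0.80, f = 0.10: q = 0.80 + 0.10 × 0.20 = 0.82. Of 250 × 0.20 = 50 expected false positives, 5 are confirmed.
- p = 0.75, f = 0.30: q = 0.75 + 0.30 × 0.25 = 0.825. Of 250 × 0.25 = 62.5 expected false positives, about 19 are confirmed.

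At p = 0.79 the chances are 0.8%, 2.2% and 5.4% for f = 0, 5% and 10%.

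**Step 4: reading the table.** The nominal one-sided error is 2.5%. With f at 10% or less, the chance of wrongly declaring success exceeds that level only for a true PPV within about 2 points below 80%; at 78% with f = 10% it is 2.5%. With larger f the exposure reaches further down.

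**Step 5: at the planning value.** If p = 0.85, declaring good performance is correct, and review bias only makes it more likely: 50.8% at f = 0 and 76.0% at f = 10%. The estimate is still inflated, by f(1 − p) = 0.10 × 0.15 = 1.5 points.

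**The case against.** The strongest reply is that the design leaves limited room for such flips. The criteria are largely numeric, and Visit 2 repeats the pressure measurement and adds visual fields, gonioscopy and corneal thickness. Attendance does not reveal the label either. Visit 2 also takes patients with "other eye diseases, vision impairment or have photographs that are unreadable who require non-emergent follow-up", and E.2.a expects that "approximately 50% of those diagnosed with eye pathology and who return for the confirmation Visit 2 will have been diagnosed with glaucoma" or as suspects. This stands as a limit on the risk. It does not close the gap at borderline discs, and it also shows that masking the specific label is feasible.

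The largest error rates at small f occur at a true PPV of exactly 80%, where a wrong declaration matters least. Adherence, not the PPV, is the trial's primary outcome. Both points argue for modest severity.

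Net inflation is not established. Under C.5.c, patients with Visit 1 pressure above 30 mmHg skip Visit 2. They would probably be confirmed, so losing them could lower the PPV by an unknown amount.

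Three stronger readings are tempting, and the documents support none of them.
- A reader might infer that the examiner was unmasked and the PPV is biased. The text is silent, and the appendices, including the reading report in Appendix F, are not available.
- A reader might infer that the conclusion can change only when the true PPV is close to 80%. That holds only for small f.
- A reader might infer that patients bring the label with them. C.6 says that they "will be notified by mail and telephoned by the study staff to schedule Visit 2", without saying that the specific diagnosis is disclosed. The result letters in Table 8 are classed as normal or abnormal, which adds little to the fact of attendance.

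**Conclusion.** The point holds as an open risk of review bias in the Aim 1 reference standard, not as a demonstrated bias. Its direction is toward a higher PPV; its size cannot be derived from the documents. The illustration rests on 250 evaluable patients and a single assumed flip rate. Under it, the chance of a wrong declaration at a true PPV of 80% rises from 2.1% to 10.7% at f = 10%, and at a true PPV of 75% it reaches 14.9% at f = 30%. The sample size and stated powers are correct and unchanged. Severity is low to moderate: one conclusion is exposed, the criteria limit the exposure, and the Aim 2 adherence outcome is untouched. It merits action because the safeguard is cheap and cannot be added afterwards.

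**What to change.** In C.6:

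1. Require the Visit 2 examiner to record glaucoma, suspect or neither before opening the Visit 1 images or report, then to open them in the same visit for patient care. Exempt emergencies.
2. Where the existing roster allows, assign an examiner who did not read that patient's Visit 1 images.
3. Add one tick box for whether the examiner already knew the Visit 1 result, through own reading, the record or the patient. Report how often it is ticked. Give the PPV without those patients as descriptive only, because they are not a random subset.

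If this is already the practice, state it in C.6. If the examinations are complete, report what examiners could see and whether readers and examiners overlapped.

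The cost is a small change in clinic workflow and record access, with no added staff or visits. Access needs attention because E.1.b links all of a patient's exams under one record number. The step does not fully mask an examiner who remembers the images, and it records disclosure by the patient without preventing it.

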During Visit 3 the eye care provider will assess the patient’s ocular, systemic, and family history and conduct a eye exam that includes: 1) best correct visual acuity measurement using Snellen eye charts, 2) slit-lamp biomicroscopy of the anterior segment, 3) intraocular pressure (IOP), 4) optic nerve head evaluation, 5) central corneal thickness measurement, 6) visual field analysis using a visual field analyzer (such as Octopus or Humphrey), and 7) gonioscopy (Table 5). Based on these results, the ophthalmologist will reconfirm their ocular diagnosis and adjust therapy as needed. Most individuals will be recommended at the appropriate follow-up intervals shown in Table 6. In conjunction with our general ophthalmology advisor and the CDC, we will plan and develop definitions of adherence for all patients during Visits 3-8. Follow-up recommendations for other eye disease diagnoses will also be made using standard *AAO Practice Pattern Guidelines*.

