**Table 6: Summary Benchmarks Preferred Practice Pattern Guidelines for POAG**

Target IOP Achieved	Progression of Damage	Duration of Control (months)	Appropriate Follow-up Interval (months)
Yes	No	<6	6
Yes	No	>6	12
Yes	Yes	NA	1-2
No	Yes	NA	1-2
No	No	NA	3-6

Source: *American Academy of Ophthalmology*

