G.1.d. Communication and Coordination with CDC: Based on Wills Eye Hospital's current CDC Cooperative Agreements, Wills Eye Investigators understand that CDC staff will be substantially involved in this 5-year research project, providing approval of the study design, definition of primary outcomes, cost analysis, data analysis, report writing, and dissemination of findings. The research team will submit proposed plans to the CDC prior to IRB submission, allowing sufficient time for review and comments by CDC staff. The CDC will be especially interested in reviewing: 1) logic models, 2) cost analysis strategies, 3) performance indicators used to monitor and evaluate projects, and 4) publications, technical reports, and manuscripts to disseminate evaluation findings. The intervention team will be available for monthly conference calls with CDC staff. Investigators are budgeted to attend two meetings each year at the CDC during the 5-year funding cycle to present progress reports and outcomes data for Specific Aims 1, 2, 3, and 4.

**In Summary:** We believe this proposed, evidence-based intervention addresses a critical gap in current patient care. It has the potential to improve detection, management, treatment, and follow-up adherence in persons at high-risk for glaucoma and other eye diseases causing vision impairment. We will design our materials so they can be replicated for communities across the nation. Our concurrent cost study is designed to estimate the feasibility of implementing the intervention in primary care offices and FQHCs, followed by referrals to local general ophthalmologists. We hypothesize that implementing telemedicine technologies for glaucoma- and ocular-disease detection will allow patients to receive care in a comfortable, convenient, and familiar setting. Our patient-centered intervention involving patient navigators and a social worker will address transportation, language, and insurance barriers and aims to improve follow-up adherence.

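### As written, the primary outcome's yearly visit quota is set once, at the year's first visit, so a change of interval within the year can misclassify patients in both directions

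*Combined protocol and SAP*

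**What the plan says.** Section E.2.b defines the Aim 2 primary outcome as "attendance at recommended follow-up visits (Visit 4 and later", summarised by year. The yearly target is fixed at one moment: "an expected number of visits will be determined based on the recommended follow-up at the first visit for that year". The counting window follows: "attendance at appointments within 13 months of the first visit will be assessed". Table 9 then gives the threshold for an adherent year: 6 visits for a 1-2 month recommendation, 3 for 3-6 months, 2 for 6 months and 1 for 12 months. E.2.c uses the resulting yes/no value for each of three years in two primary tests, one for Year 1 and one for the average of Years 2 and 3.

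The plan knows that intervals move. C.9 says "Most individuals will be recommended at the appropriate follow-up intervals shown in Table 6", and Table 6 makes the interval depend on target pressure, progression and "Duration of Control (months"). E.2.b itself accepts that recommendations will differ with pressure control, severity and procedures. Its answer is that the team, with the CDC, "will plan and develop definitions of adherence for patients during Visits 3-8". C.9 repeats the promise, and C.5.d dates it: "before we begin the study, in conjunction with our general ophthalmology advisor, we will plan and develop definitions of adherence". G.1.d gives CDC staff a role in "providing approval of the study design, definition of primary outcomes". No such definition appears in the documents.

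**The concern.** The outcome is meant to show whether patients kept the visits they were told to make. A quota fixed at the start of the year measures that only if the recommendation stays the same until the year ends. If the interval is lengthened, fewer visits are due than the quota demands, and perfect attendance can fail. If it is shortened, more visits are due than the quota demands, and a patient who misses several can pass. The quota is renewed each year, but that does not help with a change inside the year.

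Both primary tests rest on this score. It is also not safe to assume that the errors fall equally on the two arms. A recommendation can change only at a visit that was attended, and attendance is what the intervention is meant to alter.

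**Working it through.** **Inputs.** Quotas of 6, 3, 2 and 1 come from Table 9, and the 13-month window from E.2.b. Visits are taken to be kept exactly on time. A return is any visit after the first of the year; add 1 to each count if the first visit counts.

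**1. Table 9 with no change of interval.** Returns = whole-number part of 13 / interval.
- 2 months: 13/2 = 6.5, so 6 (quota 6)
- 4 months: 13/4 = 3.25, so 3 (quota 3)
- 6 months: 13/6 = 2.17, so 2 (quota 2)
- 12 months: 13/12 = 1.08, so 1 (quota 1)

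At these intervals the quotas match full attendance with the first visit left out. At the long end of the 3-6 month row they do not: 13/5 = 2.6, so 2 against 3.

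**2. Interval lengthened, 1-2 to 6 months, every visit kept.** With starting interval a and the change made at return k, returns = k + whole-number part of (13 - ka)/6.

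| Change at return | a = 1 month | a = 2 months | Quota |
|---|---|---|---|
| 1 | 1 + 12/6 = 3 | 1 + 11/6, so 2 | 6 |
| 2 | 2 + 11/6, so 3 | 2 + 9/6, so 3 | 6 |
| 3 | 3 + 10/6, so 4 | 3 + 7/6, so 4 | 6 |

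The range is 2-4 returns, or 3-5 visits with the first included. Every cell falls short of 6 on either count.

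**3. Interval shortened, 6 to 1-2 months at month 6.** At the two-month limit, visits fall due by months 6, 8, 10 and 12, so four are due (more at shorter spacing). The quota is still 2. Keeping two and missing two is scored adherent. If the first visit counts, a single return is enough.

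**4. Paths that depend on how the first visit is treated.**
- 6 to 12 months at the first return: one return (month 6) against 2. With the first visit, 2 against 2.
- 3-6 to 6 months at the first return, for example months 3 and 9: two returns against 3. With the first visit, 3 against 3.

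Both fall short only if the first visit is left out. The restriction to Visit 4 and later points that way for Year 1, if Visit 3 is that year's first visit. For Years 2 and 3 the text is silent.

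**5. Power.** Table 10 reproduces with 135 per group, two-sided alpha 0.025 and a pooled chi-square test: 86.1, 85.7, 86.1, 87.2, 89.1 and 91.6% against the printed 86, 86, 86, 87, 89 and 92%. It takes the adherence proportions as given, so nothing above changes it unless misclassification rates are assumed, and the documents supply none.

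**The case against.** The best reply is that the plan sees the problem and defers it. Straight after stating the rule it concedes that recommendations will vary and promises definitions, so Table 9 may be provisional. The appendices are not in the text reviewed, and the definition may exist. This is why the point is limited to the rule as written and why filing the definition comes first. But no other rule for scoring a year is given, and the promise does not say that within-year changes will be covered.

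A second reply is that a start-of-year target is a reasonable design: it is renewed annually and limits reliance on later information that only attenders generate. That is a real advantage, and re-setting the count gives up some of it. The fixed quota nevertheless already depends on one post-randomisation recommendation each year, and it pays for its simplicity with the errors in steps 2 and 3.

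A third reply concerns reach. Table 6 is for primary open-angle glaucoma, and other diagnoses follow other guidance. In the preliminary data (Table 3), 52 of 1,290 people had newly found glaucoma and 276 were suspects. C.9 does send most patients to Table 6, but no distribution of intervals or of changes is given. This objection stands as a limit on size.

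A reader might also infer that a stable patient following Table 6 from 6 to 12 months must fail. The documents do not support that. It needs the first visit left out, and it assumes that control has passed 6 months by the month-6 return, whereas Table 6 lists only below 6 and above 6.

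The quota-free measures do not replace the primary outcome. The rate of kept appointments in E.2.e is secondary, and the share of visits attended in Table 7 is a tracking measure.

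**Conclusion.** The point holds for the rule as written and should be fixed. Two errors follow by counting and do not depend on the treatment of the first visit: full attenders moved from 1-2 to 6 months at any of the first three returns are scored non-adherent, and patients moved from 6 to 1-2 months at month 6 can miss two of four due visits and be scored adherent. The shortfalls in step 4 are conditional.

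A reader might go on to infer a biased relative risk or lost power. The documents do not support either. They do not show how often intervals change within a year, in which direction, or in which arm, so neither the number of patients affected nor any effect on the primary tests can be determined. The conclusion assumes on-time visits and that no filed definition already covers within-year changes.

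**What to change.** If the promised definition exists and covers within-year changes, file it with its date.

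If not, settle the following before outcome data are reviewed. Keep the annual yes/no outcome and Table 9's quotas, but re-set the expected count at each attended visit where the recommendation changes:

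Expected = whole-number part of the sum, over each stretch of the 13-month window, of (months in the stretch x Table 9 quota then in force / 12).

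- **No change:** 13 x 6/12 = 6.5, 13 x 3/12 = 3.25, 13 x 2/12 = 2.17 and 13 x 1/12 = 1.08 give 6, 3, 2 and 1, which are Table 9's own values.
- **1-2 moved to 6 at month 2:** 2 x 6/12 + 11 x 2/12 = 2.83, so 2 expected. Two are kept (months 2 and 8): adherent.
- **6 moved to 1-2 at month 6:** 6 x 2/12 + 7 x 6/12 = 4.5, so 4 expected. Two are kept (three with the first visit): non-adherent.

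State whether the window's first visit counts, and apply the same answer in every year. Keep Table 9 with the fixed quota as a sensitivity analysis.

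The cost is SAP wording and some programming. Recommended intervals and kept or missed visits are already tracked (Table 8, E.1.c). The outcome will depend more on recommendations made after randomisation; the sensitivity analysis will show how much that matters. Some full attenders at the long end of the 3-6 month range will still fall short, as they do under Table 9's quota of 3 if the first visit is not counted. Only the scoring changes, not any clinical interval.
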